7.4.2 Exclusion Criteria

Table 2 shows the exclusion criteria that will be used prospectively in the PrismRA arm and the best approximation for the selection of comparable patients in the observational external control arm.

Table 2. Exclusion criteria by study arm

	PrismRA arm	External control arm
1	Patient has any non-study limitation precluding patient receipt of the PrismRA test (e.g., financial, or logistical limitations).	The assumption will be made that patients who used b/tsDMARDs did not have such limitations that would have prevented the potential receipt of the PrismRA test had it been offered.
2	Concurrent treatment with an investigational product or use of an investigational product less than 4 weeks prior to Visit 1.	This criterion is not replicable with real world dispensing data and will not be used.
3	Patient cannot have participated in an observational study at least 4 weeks prior to Visit 1.	This criterion is not replicable in real-world data and will not be used.
4	The use of RA therapies outside of FDA-approved indication.	This criterion is not replicable with real-world dispensing data and will not be used.

5	Patient has been previously exposed to any non-TNFi b/tsDMARDs (FDA approved or experimental).	
Patients who have been previously exposed to any non-TNFi b/tsDMARDs any time during their history prior to the study treatment initiation will be excluded.
 
The list of non-TNFi b/tsDMARDs approved for RA includes the following:
 
 • IL-6i (tocilizumab, sarilumab) • IL-1i (anakinra) • T-cell co-stimulation inhibitor (abatacept) • B-cell depletion agent (rituximab) • JAKi (tofacitinib, baricitinib, upadacitinib) 
The list of non-TNFi b/tsDMARDs not currently approved for RA includes the following:
 
 • IL-23i (guselkumab, risankizumab, tildrakizumab, ustekinumab [IL-12/IL-23i]) • IL-17i (secukinumab, ixekizumab, brodalumab)
6	Women who are known to be pregnant or breast-feeding or plan to get pregnant during the study.	Patients who have relevant pregnancy-related codes in the past 12 months or during the 24-week follow-up will be excluded.
7	Patient is currently receiving systemic antimicrobial treatment for viral, bacterial, fungal, or parasitic infection at the time of Visit 1.	Patients who received antimicrobial medications in the 30-day period prior to the b/tsDMARD initiation will be excluded.

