8.1 Pre-Screening

PrismRA arm:

Prior to Visit 1, potential patient charts may be reviewed to determine eligibility for the study. At the discretion of the Investigator, pre-screening lab tests (i.e., Complete Blood Count (CBC), Clinical Metabolic Panel (CMP), Tuberculosis (TB), and/or C-reactive Protein (CRP)) may be ordered and analyzed per standard of care if the patient has not already received these lab tests within 3 months of the planned study Visit 1.

External control arm:

The entirety of data for each patient (no less than 12 months) prior to the study treatment initiation will be used to assess their medical history and past medication use and to determine their eligibility (see above). For variables required to be up to date at the time of the study treatment initiation, the most recent value within the 3-month period prior to the study treatment initiation will be used, unless otherwise stated (see Table 1, Table 2).

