8.5 Schedule of Visits

PrismRA arm:

The timing for the follow-up visits (visits 3 and 4) should be projected based on the date of Study Treatment Initiation (index date).

External control arm:

The date of study treatment initiation constitutes the index date for the beginning of the follow-up. The 3-month period prior to the index date will be used to ascertain the baseline CDAI. The 12-week follow-up will be defined as the clinical encounter closest to the 12-week time point within the 12 (\pm 4) week visit window. The 24-week follow-up will be defined the visit closest to the 24-week time point within the 24 (\pm 4) week visit window. Depending on feasibility, we will

attempt follow-up windows, such as \pm 6 week window, \pm 3 week window, and \pm 2 week window. Sensitivity analyses with different follow-up windows will be conducted as needed.

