For the primary efficacy analysis multiple imputation (MI) will be used with the assumption that patients with unreported outcome measures at 12 and 24 weeks have outcome events that are non-informative under the missing at random (MAR) assumption. This assumes that missingness occurs independent of the unobserved outcome: that is, the possibly unknown true outcome for a patient is the same regardless of whether it is actually observed. This assumption underlies the ITT principle, which analyses all eligible patients according to the treatment group to which they were assigned regardless of subsequent missingness.

For all approaches using MI, fully conditional specification (FCS) methods will be used, which assume the existence of a joint distribution for all variables. [10] All eligible patients meeting inclusion and exclusion criteria and initiating the study treatment will be used to impute missing observations. Imputation models will include all relevant available observations at baseline and 12 and 24 week follow up visits. Separate MI models will be used to create m imputed datasets for each study arm and combined into m analysis datasets with complete data. The choice of m will be determined by the fraction of missing information in the variables to be imputed. [11] MI performed separately within each study arm maintains the structure of the missing data patterns and the relationship between covariates specific to each database and ensures that no outcome information is used in PS matching. [12] Each imputation model will include all covariates listed in Table 4 of Section 6.2 along with the dependent variables and continuous scores for each study outcome as specified in Section 3.0. Dichotomous endpoints will be derived based on continuous scores within each imputed dataset. Analyses will proceed as described in Sections 6.3 and 6.4 using each of the imputed datasets. Finally, treatment effect estimates will be averaged using Rubin's rule [13] to obtain a pooled estimate with standard errors.

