5.5 Statistical Bias Reduction

Studies using observational data are prone to multiple biases. These potential biases in this study are addressed as described below.

Selection Bias. To minimize selection bias for identifying an external control arm for a clinical trial, the study was designed using the target trial emulation framework. [14] The external control arm inclusion/exclusion criteria are carefully defined and matched to the PrismRA arm to reduce potential selection bias. All available patients in the external control arm meeting the criteria for selection will be used in the analyses.

The design of the study is aimed to emulate a randomized clinical trial as closely as possible. In a randomized clinical trial, on average, treated and control groups are balanced with respect to pre-treatment characteristics. The analysis of the entire randomized sample will give the unbiased estimate of the causal effect in the entire trial eligible population. Any "selection" of individuals after randomization could lead to covariate imbalance, change in the population for whom the result may apply, and biased treatment effect estimates. PS methods attempt to emulate the process of randomization by using only pre-treatment covariates (blinded to outcomes and other follow-up observations) to control for potential confounding. We propose a PS model building

process that will estimate a PS for each patient in the entire eligible cohort to be used in analyses of all study objectives.

Information bias. Observational studies relying on retrospective data collection are at risk of information bias, as the accurate assessment of exposures, outcomes and key covariates may be challenged by issues such as the timing of clinical assessments, criteria for treatment response, and documentation in the EMR that vary between and within sites. Objective measures of outcomes and other variables at predefined time points will be used where possible. All data for eligible patients will be extracted and data from multiple sources will be deterministically linked to create a more complete capture of the patient journey. For the external control arm, information on confounders will be limited to data as it is documented in the patient's record.

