6	Women who are known to be pregnant or breast-feeding or plan to get pregnant during the study.	Patients who have relevant pregnancy-related codes in the past 12 months or during the 24-week follow-up will be excluded.
7	Patient is currently receiving systemic antimicrobial treatment for viral, bacterial, fungal, or parasitic infection at the time of Visit 1.	Patients who received antimicrobial medications in the 30-day period prior to the b/tsDMARD initiation will be excluded.
8	Patient has any active, chronic, or recurrent invasive infection (e.g., listeriosis and histoplasmosis) and/or a viral infection, that based on the Investigator's clinical assessment, makes the patient an unsuitable candidate for the study. This includes hepatitis B virus (HBV) or hepatitis C virus (HCV), recurrent or disseminated (even a single episode) herpes zoster, disseminated (even a single episode) herpes simplex, or human immunodeficiency virus (HIV).	Patients with the relevant diagnostic codes for chronic, or recurrent invasive infections any time prior to the study treatment initiation will be excluded. This includes listeriosis, histoplasmosis, coccidioidomycosis, tuberculosis, non-tuberculosis mycobacterial infections, cryptococcosis, pneumocystis pneumonia, toxoplasmosis, HBV, HCV, varicella zoster virus (VZV), herpes simplex virus (HSV), HIV.
9	Patients with malignancy except non-melanoma skin cancer, localized prostate cancer treated with curative intent with no evidence of progression, low risk or very low risk (per standard guidelines) localized prostate cancer under surveillance/watchful waiting (without intent to treat), or carcinoma in situ of any type (complete resected).	Patients with cancer diagnostic codes any time prior to the study treatment initiation will be excluded. This includes all malignancies except non-melanoma skin cancer. Allowing for localized and cured cancers is not replicable in real-world data and will not be attempted.

10	Patients who are unable to understand the protocol and unable to provide informed consent.	This criterion is not replicable in real-world data and will not be used.
11	Patients who are not indicated for PrismRA.	
This criterion is not replicable in real-world data and will not be used.
 
This study assumes that the careful replication of the above inclusion and exclusion criteria will ensure a comparable indication for PrismRA in the external control arm.

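### External controls are excluded for pregnancy codes recorded after the index date, so their eligibility depends partly on follow-up data; PrismRA eligibility does not. The effect is probably small.

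*Protocol*

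**What the plan says.** - **Control rule.** Protocol 7.4.2, Table 2 row 6: "Patients who have relevant pregnancy-related codes in the past 12 months or during the 24-week follow-up will be excluded". SAP 6.1.2, Table 3 row 6 has the same rule: "in the past 12 months or during the 24-week follow-up will be excluded". It is therefore current in both documents.
- **PrismRA counterpart**, same row: "Women who are known to be pregnant or breast-feeding or plan to get pregnant during the study". The Protocol 8.6 schedule places the eligibility check at Visit 1 only.
- **Time zero for controls**, Protocol 8.5: "The date of study treatment initiation constitutes the index date for the beginning of the follow-up".
- **Data for control eligibility**, Protocol 8.1: at least 12 months of data "prior to the study treatment initiation will be used to assess their medical history and past medication use and to determine their eligibility".
- **Principle on later selection.** SAP 5.5 presents the design as an emulation of a randomized trial and warns that selection "of individuals after randomization could lead to covariate imbalance, change in the population for whom the result may apply, and biased treatment effect estimates". It describes the propensity score methods as "using only pre-treatment covariates (blinded to outcomes and other follow-up observations) to control for potential confounding".

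**The concern.** In an emulated trial, eligibility should be settled with what is known at time zero. Row 6 lets an event in the 24 weeks after the index date remove a control from the cohort. The PrismRA criterion looks at known status and stated intention at screening. Two women with the same history and the same unplanned pregnancy after starting treatment would therefore be treated differently: the control is removed and the PrismRA patient is analysed.

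At stake is the comparability of the arms. If the removed women differ in response from the other controls, the control proportion shifts for a reason unrelated to the test. Propensity score matching on baseline covariates cannot be relied on to undo selection on a later event.

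**Working it through.** **Step 1: the passages side by side.**

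| Question | PrismRA arm | External control arm |
|---|---|---|
| When is pregnancy assessed for eligibility? | Visit 1 (Protocol 8.6) | 12 months before the index date and 24 weeks after it (row 6) |
| What is assessed? | Known pregnancy or breast-feeding, stated plan | A recorded code |
| Unplanned pregnancy after initiation? | No passage removes the patient from analysis | Excluded if coded |

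For PrismRA, withdrawal under Protocol 8.11 is discretionary. SAP 1.0 and 5.2 define the modified ITT population by eligibility and treatment initiation. SAP 5.4 and 6.3 impute missing outcomes for all such patients. An initiator who later becomes pregnant is therefore still analysed.

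The other patient-history exclusions applied to controls in Table 2 (rows 5, 7, 8 and 9) all look back from treatment initiation. Among the listed exclusions, only row 6 looks at the patient's follow-up.

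**Step 2: the plan's own figure.** Inputs from Protocol 10.1: 600 and 1,500 patients, attrition 45% and 50%, response 40% and 30%, two-sided alpha 0.05, Fisher's exact test.

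- Evaluable patients: 600 × 0.55 = 330 and 1,500 × 0.50 = 750.
- Exact Fisher power: 88.4%, against the stated 88%. Reproduced.

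**Step 3: loss of numbers.** The documents do not say how many controls the post-index part removes. If it removes 1% of evaluable controls, 750 becomes 742 and power is 88.5% (the test is discrete, so small changes are not monotone). If it removes 5%, 712 remain and power is 87.9%. Sample size is not the issue.

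**Step 4: shift in the control proportion.** Let f be the share of controls removed and g the gap in response between retained and removed controls. The full-cohort rate equals the retained rate minus f × g, so removal raises the control rate by f × g.

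- Low case (assumed f = 0.2%, g = 20 points): 0.002 × 20 = 0.04 points.
- High case (assumed f = 1%, g = 30 points): 0.01 × 30 = 0.3 points.

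Per 1,500 controls, these shares are 3 and 15 women.

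**Step 5: direction and a wider range.** Take a full-cohort control rate of 30% and let r be the response rate of the removed women. The retained rate is (0.30 − f·r)/(1 − f). Change in the arm difference, in points:

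| f (assumed) | r = 0% | r = 30% | r = 60% |
|---|---|---|---|
| 0.5% | −0.15 | 0 | +0.15 |
| 1% | −0.30 | 0 | +0.30 |
| 2% | −0.61 | 0 | +0.61 |
| 5% | −1.58 | 0 | +1.58 |

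By the normal approximation, power without any exclusion is 89.1%. At f = 1% it becomes 87.0% (r = 0%) or 90.8% (r = 60%). At f = 5%, well beyond the share assumed in Step 4, it becomes 75.6% or 95.8%. The effect is small if the share is small, but only a count can show that.

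These figures ignore matching and imputation. They indicate scale only.

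**The case against.** The strongest defence is that row 6 serves a purpose. The table offers best approximations of the trial criteria, and intention to conceive is not among the control data elements in Protocol 8.6. A code during follow-up is a proxy for a planned pregnancy, and it can also reveal one that was present but uncoded at the index date. Deleting the clause gives up both. This stands, and it is the real cost of the fix.

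It does not rescue the rule. A realised pregnancy is not a baseline intention: the proxy removes unplanned pregnancies and keeps women who planned but did not conceive. It also catches only controls who remain in the data long enough to be coded. Where a criterion cannot be replicated, the same table usually says so and does not use it (rows 2, 3, 4, 10 and 11).

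A second defence is that the SAP 5.5 sentence concerns randomized trials, that its remark on pre-treatment covariates concerns the propensity score, and that Protocol 8.1 does not say that only pre-index data may be used. The first two points are fair, so the conflict with SAP 5.5 is by analogy. The third has some force, since Protocol 8.1 refers back to the criteria. Even so, it names pre-initiation data as the basis for eligibility, and row 6 goes beyond that. Nor does the ITT statement in SAP 5.4 settle the matter: it covers a principle "which analyses all eligible patients according to the treatment group to which they were assigned regardless of subsequent missingness", which presupposes that eligibility has already been decided.

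A reader might infer that the rule lifts control response because pregnant women stop treatment. The documents do not support this. No passage says how such women respond, and SAP 3.0 defines the composite by treatment switch without stating clearly whether stopping alone counts as failure.

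**Conclusion.** The point holds as a minor design flaw. Part of a control exclusion is decided after time zero, with no equivalent post-initiation exclusion in the PrismRA arm, and it needs reconciling with Protocol 8.1 and SAP 5.5.

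The size is unknown and probably small: at most about 0.3 points in the control proportion if no more than 1% of controls are affected and the response gap is no more than 30 points. Both inputs are assumptions. The direction is not fixed. If the removed women respond less often, the control rate rises and the rule works against PrismRA; if they respond more often, it works in its favour.

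Two stronger readings should be resisted. A reader might infer that the emulation of a target trial fails; a shift of this size does not support that. A reader might also infer that pregnancy during the study is ignored in the PrismRA arm; it is not, because planned pregnancy is an exclusion there. The asymmetry lies between a stated intention and a later event.

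**What to change.** 1. In row 6 of both tables, delete the part that refers to the 24-week follow-up and keep the 12-month look-back, so that eligibility for the main cohort rests on data up to the index date.
2. State that planned pregnancy is not replicable in real-world data, as the tables do for other such criteria.
3. Handle pregnancy during follow-up the same way in both arms in the analysis, for example as a named intercurrent event.
4. Report the number of controls with post-index pregnancy codes and run one sensitivity analysis that excludes them.

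The cost is mainly two wording edits, one line of cohort code and one extra run. The downside is that the main cohort loses an imperfect proxy for planned pregnancy and may keep a few controls whose pregnancy was present but uncoded at the index date. The sensitivity analysis covers this.

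The same revision should look at Protocol 8.10, which allows a CDAI during follow-up to be required of controls as needed. That is also a post-index condition on controls.

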JAKi	Janus Kinase inhibitor
MCID	Minimal Clinically Important Difference
MID	Minimal Important Difference
MOA	Mechanism of Action
MTX	Methotrexate
NSAIDs	Non-Steroidal Anti-Inflammatory Drug
PRO	Patient Reported Outcomes
PtGA	Patient Global Assessment

Abbreviation or Specialist Term	Explanation
RA	Rheumatoid Arthritis
RAPID3	Routine Assessment of Patient Index Data 3
RDCI	Rheumatic Disease Comorbidity Index
RNA	Ribonucleic Acid
SAE	Serious Adverse Event
SD	Standard Deviation
SOC	Standard of Care
TB	Tuberculosis
TNFi	Tumor Necrosis Factor Inhibitor
tsDMARD	Targeted small molecule Synthetic Disease Modifying Anti-Rheumatic Drug
UADE	Unanticipated Adverse Device Effect
US	United States

4 Definitions

Terms	Definition of Terms
DRIVE Study	The comparative effectiveness study of the PrismRA test comparing the clinical outcomes of patients in the PrismRA arm (trial) and the external control arm (observational).
Baseline	Assessments of patients as they enter the PrismRA arm. For the external control arm, the corresponding baseline CDAI assessment window is the 3-month period before the index date (defined as the time of study treatment initiation). For medical history all available data before the index date will be used in the external control arm.
Enrollment	The point at which the patient signs the informed consent form for the PrismRA arm. Not applicable for the external control arm.
PrismRA arm	Trial participants in the trial conducted by Scipher Medicine for whom PrismRA test is performed and the Investigator will use the PrismRA test results to inform the treatment decision.
External control arm	OM1 real-world data patients who received standard of care treatment for RA with TNFi or non-TNFi b/tsDMARDs without guidance from PrismRA test results.
Study Treatment	The b/tsDMARDs (FDA approved for RA) that is initiated at Visit 2 (See Section 8.5), informed by the PrismRA test in the PrismRA arm and as a part of standard of care in the external control arm. This study treatment (b/tsDMARDs) can be the very first b/tsDMARD for the patient or a subsequent b/tsDMARD after having used one or more TNFi bDMARDs (but not non-TNFi b/tsDMARDs).
Study Treatment Initiation	The point at which a study treatment (See “Study Treatment” above) is initiated to treat RA. This time point constitutes the index date (beginning of the follow-up) and is defined as Visit 2

Terms	Definition of Terms

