6.1 Study Type

This is a two-arm, multi-center United States (U.S.)-based study with a prospective, non-blinded intervention arm (PrismRA arm) and an observational external control arm designed to demonstrate the clinical utility of the PrismRA test in routine clinical care. The study will compare outcomes for RA patients with moderate to high disease activity whose treatment is informed by PrismRA test results (PrismRA arm) to outcomes among RA patients who receive the standard of care (SOC) not informed by PrismRA results (external control arm).

PrismRA arm:

In this arm, all patients will receive the PrismRA test. The Investigator will receive the PrismRA results and use those results to inform treatment selection by Visit 2. Patients may be followed indefinitely from the time of signing the informed consent and medical records release form unless the patient withdraws from the study, dies, or becomes lost to follow-up. Changes to the study b/tsDMARDs do not terminate follow-up. A patient can withdraw from the study at any time.

External control arm:

The observational external control arm will consist of comparable initiators of b/tsDMARDs in OM1's PremiOM RA dataset, in which the specific choice of TNFi or non-TNFi b/tsDMARDs was based on the treating physician's clinical judgement and was not informed by the PrismRA test results. Baseline as well as follow-up data will consist of data obtained at routine clinical encounters. The index date (start of follow-up) for this external control arm will be defined as the time of initiation of the study treatment (very first or subsequent b/tsDMARDs) and patients will be followed until week 24, death, or loss to follow-up, whichever occurs first. Changes to the

study b/tsDMARDs do not terminate follow-up. Controls may be sampled from time intervals contemporaneous with the trial (March 2022 and onward) as well as historical periods.

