8	
Patient has any active, chronic, or recurrent invasive infection (e.g., listeriosis and histoplasmosis) and/or a viral infection, that based on the Investigator's clinical assessment, makes the patient an unsuitable candidate for the study. This includes hepatitis B virus (HBV) or hepatitis C virus (HCV), recurrent or disseminated (even a single episode) herpes zoster, disseminated (even a single episode) herpes simplex, or human immunodeficiency virus (HIV).
	
Patients with the relevant diagnostic codes for chronic, or recurrent invasive infections any time prior to the study treatment initiation.
 
This includes listeriosis, histoplasmosis, coccidioidomycosis, tuberculosis, non-tuberculosis mycobacterial infections, cryptococcosis, pneumocystis pneumonia, toxoplasmosis, HBV, HCV, varicella zoster virus (VZV), herpes simplex virus (HSV), HIV.

9	
Patients with malignancy except non-melanoma skin cancer, localized prostate cancer treated with curative intent with no evidence of progression, low risk or very low risk (per standard guidelines) localized prostate cancer under surveillance/watchful waiting (without intent to treat), or carcinoma in situ of any type (complete resected).
	
Patients with cancer diagnostic codes any time prior to the study treatment initiation will be excluded. This includes all malignancies except non-melanoma skin cancer.
 
Allowing for localized and cured cancers is not replicable in real-world data and will not be attempted.

10	
Patients who are unable to understand the protocol and unable to provide informed consent.
	
This criterion is not replicable in real-world data and will not be used.

11	
Patients who are not indicated for PrismRA.
	
This criterion is not replicable in real-world data and will not be used.
 
The assumption will be made that the careful replication of the above inclusion and exclusion criteria will ensure a comparable indication for PrismRA in the external control arm.

12	
This point does not apply to the PrismRA arm.
	
Patients will be excluded if they have been cared for by rheumatologists who have participated in the PrismRA arm any time in the past to avoid including patients using PrismRA.

8 Study Procedures

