9.1 Introduction to Safety Assessments

PrismRA arm:

There are no investigational therapies being evaluated per the protocol. For patients in the informed treatment selection arm, Investigators will receive the PrismRA test results and use the results to inform their treatment decision. PrismRA was developed and its performance characteristics determined by Scipher Medicine. The laboratory is certified under CLIA and accredited under CAP. This commercially available test is used for clinical purposes. It should not be regarded as investigational, or for research. The Investigator is expected to follow all aspects of the prescribing information when administering a pharmaceutical therapy in the course of the treatment of patients included in this study.

External control arm:

Data arise from routine clinical practice and are not subject to study-specific safety assessment.

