9.2 Anticipated and Unanticipated Adverse Device Effects

PrismRA arm:

PrismRA is not expected to result in either anticipated or unanticipated adverse device effects (UADE) as it involves the analysis of ex-vivo blood samples from the participating patients.

This study does include a potential source of harm to the patient as a result of the venipuncture procedure, unrelated to the study device:

- Faintness, inflammation of the vein, bruising, temporary discomfort, and bleeding at the site of puncture may occur.
- Infection may also occur, though rare.

External control arm:

Data arise from routine clinical practice and do not involve the use of the PrismRA test. Thus, no study-relevant adverse device effect exists.

10 Statistical Considerations

Data collected throughout this study will be analyzed by Sponsor or its designee.

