6.1.2 Exclusion Criteria

Table 3. describes the exclusion criteria that will be used prospectively in the PrismRA arm and their best approximation for the selection of comparable patients in the observational external control arm.

In addition to the exclusion criteria outlined below, this study will exclude patients in the external control arm that are managed by physicians participating in the PrismRA arm to avoid potential for contamination bias (e.g., erroneous inclusion of patients who received PrismRA). Patients whose study treatment initiation is managed by PrismRA physicians identified by National Provider Identifier (NPI) will be excluded from eligibility.

Table 3. Exclusion criteria by study arm

PrismRA arm	External control arm

1	Patient has any non-study limitation precluding patient receipt of the PrismRA test (e.g., financial, or logistical limitations).	It assumes patients who used b/tsDMARDs did not have such limitations that would have prevented the potential receipt of the PrismRA test had it been offered.
2	Concurrent treatment with an investigational product or use of an investigational product less than 4 weeks prior to Visit 1.	This criterion is not replicable with real world dispensing data and will not be used.
3	Patient cannot have participated in an observational study at least 4 weeks prior to Visit 1.	This criterion is not replicable in real-world data and will not be used.
4	The use of RA therapies outside of FDA-approved indication.	This criterion is not replicable with real-world dispensing data and will not be used.
5	Patient has been previously exposed to any non-TNFi b/tsDMARDs (FDA approved or experimental).	
Patients who have been previously exposed to any non-TNFi b/tsDMARDs any time during their history prior to the study treatment initiation will be excluded.
 
The list of non-TNFi b/tsDMARDs approved for RA includes the following:
 
IL-6i (tocilizumab, sarilumab)
 
IL-1i (anakinra)
 
T-cell co-stimulation inhibitor (abatacept)
 
B-cell depletion agent (rituximab)
 
JAKi (tofacitinib, baricitinib, upadacitinib)
 
The list of non-TNFi b/tsDMARDs not currently approved for RA includes the following:

		IL-23i (guselkumab, risankizumab, tildrakizumab, ustekinumab [IL-12/IL-23i]) IL-17i (secukinumab, ixekizumab, brodalumab)

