12	This point does not apply to the PrismRA arm.	Patients cared for by rheumatologists who have participated in the PrismRA arm any time in the past will be excluded to avoid including patients using PrismRA.

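### Controls are screened for PrismRA use only through trial physicians, so a control treated on a commercially ordered PrismRA result could enter undetected

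*Protocol*

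**What the plan says.** Protocol section 4 defines the external control arm as "OM1 real-world data patients who received standard of care treatment for RA with TNFi or non-TNFi b/tsDMARDs without guidance from PrismRA test results". Protocol 9.2 adds, for the same arm, "Data arise from routine clinical practice and do not involve the use of the PrismRA test".

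One eligibility rule puts this into practice. Protocol Table 2, row 12 reads "Patients will be excluded if they have been cared for by rheumatologists who have participated in the PrismRA arm any time in the past", and SAP Table 3, row 12 matches it: "Patients cared for by rheumatologists who have participated in the PrismRA arm any time in the past will be excluded". The text of SAP 6.1.2 gives contamination bias as the reason and describes the mechanism as "Patients whose study treatment initiation is managed by PrismRA physicians identified by National Provider Identifier (NPI) will be excluded from eligibility".

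On availability outside the trial, Protocol 9.1 states: "This commercially available test is used for clinical purposes". On the control period, Protocol 6.1 states: "Controls may be sampled from time intervals contemporaneous with the trial (March 2022 and onward) as well as historical periods". Protocol 6.2 and SAP 5.2 use the contemporaneous period first and go back to earlier years only if needed.

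**The concern.** The plan recognises contamination of the comparator and closes one route to it, the trial physicians. By the protocol's own account there is a second route. A rheumatologist outside the roughly 33 sites could order the test commercially, act on the result and start a b/tsDMARD. Nothing in the selection steps would find that patient, who would then be counted as standard of care.

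This is crossover in the comparator. If PrismRA-guided care is better, tested controls raise the control response rate and shrink the estimated effect. The exploratory comparison of TNFi and non-TNFi shares would also draw together. What is at stake is how a null or small effect is read: the plan gives no means of telling limited clinical utility from a control arm that partly received the intervention.

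**Working it through.** **Step 1: is there any other screen?** These are the places where one could stand.

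- Eligibility tables (Protocol 7.4; SAP 6.1.1 and 6.1.2): only row 12 concerns PrismRA use. Row 1 of the exclusions assumes that controls faced no barrier to receiving the test, which does not help.
- Control-arm data table (Protocol 8.6): PrismRA is marked as not applicable, so it is not extracted.
- Data source (Protocol 6.2; SAP 5.2): linked claims, EMR and laboratory results are available, but no search of them for the test is planned.
- Limitations (Protocol 11.1 and 11.2): PrismRA use outside the trial is not mentioned.
- Sensitivity and future analyses (SAP 6.3.2, 6.4.2 and 8.0): complete-case, censoring-weight and tipping-point analyses only.

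So the control-arm definition is enforced only through the physician rule.

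**Step 2: does the timing overlap?** The latest revision listed in the protocol took effect on 20 October 2022, and its current text calls the test commercially available. That date lies inside the control window opening in March 2022. The documents give no launch date, so they do not show that historical controls are free of the test either.

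**Step 3: reproduce the stated power.** Inputs from Protocol 10.1: 600 and 1,500 patients, attrition 45% and 50%, response 40% and 30%, Fisher's exact test, two-sided alpha 0.05.

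- Evaluable: 600 × (1 − 0.45) = 330 and 1,500 × (1 − 0.50) = 750.
- Power by exact enumeration of Fisher's test: 88.4%, against 88% stated. The figure reproduces.

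**Step 4: dilution.** Let c be the share of controls treated on a PrismRA result. The documents do not give c; the range below is assumed. Each such control is taken to gain the full planned 10 points.

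- Control response = 0.30 + 0.10c
- Expected difference = 0.40 − (0.30 + 0.10c) = 0.10 × (1 − c)

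| c | Control response | Difference (points) | Power, 330 vs 750 |
|---|---|---|---|
| 0% | 30.0% | 10.0 | 88.4% |
| 5% | 30.5% | 9.5 | 84.8% |
| 10% | 31.0% | 9.0 | 80.6% |
| 15% | 31.5% | 8.5 | 75.8% |
| 20% | 32.0% | 8.0 | 70.4% |
| 30% | 33.0% | 7.0 | 58.5% |

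Power drops below 80% at about c = 11% (79.7%).

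If only half the controls were contemporaneous and 10% or 20% of those had been tested (both assumed, with no testing among the rest), c would be 0.5 × 10% = 5% or 0.5 × 20% = 10%.

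SAP 6.3 aims for about twice as many matched controls as PrismRA patients. That is 2 × 600 = 1,200, or 600 evaluable at 50% attrition. With 330 vs 600, power is about 86% at c = 0, 82% at 5%, 77% at 10% and 67% at 20%.

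All these powers are illustrative. The planned analysis is variable-ratio matching, multiple imputation and weighted logistic regression, not Fisher's test on complete cases.

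**The case against.** A reader might infer that the plan admits tested patients as controls. It does not: a patient whose treatment was guided by PrismRA fails the definition in Protocol section 4. The gap is one of verification, since the definition is applied only through a proxy that covers trial physicians.

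A reader might also infer that a null result would be uninterpretable. The documents do not support that. They give no uptake figure, and at c = 5% the expected difference is still 9.5 points. The bias is also conservative if the test works, so it cannot produce a false claim of superiority.

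The full-benefit assumption is fairly called upper-end. SAP 5.2 plans a separate PrismRA-adherent population because some tested patients will start a TNFi despite a non-response signature. The planned 10 points is an arm-wide figure and already averages over such patients, but physicians outside the trial may follow the result less often than the investigators do.

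Finally, it is tempting to exclude from the main analysis every later patient of any physician who has ever ordered PrismRA. That would also remove untested patients and tilt the controls toward prescribers who have not adopted the test. SAP Table 4 has no prescriber or practice covariate to adjust for this. Losing contemporaneous controls could also trigger the wider historical window under the 95% retention rule in SAP 5.2, which the plan tries to keep small because of secular trends. This objection stands, and the physician-wide rule belongs in a sensitivity analysis.

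None of these points supplies the missing patient-level check.

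**Conclusion.** The gap is real. Controls are defined by the absence of PrismRA guidance, the test can be had outside the trial, and the plan as written would not detect a control treated on a commercial result. The contemporaneous period is the most plausible place for this, but the documents do not demonstrate it.

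The size is unknown. Under the upper-end assumption the effect on power is modest at low use: about 85% at c = 5% and 81% at c = 10%. It becomes material at higher use, with 70% at c = 20%. The direction is toward no difference if the test helps. The confidence is in the gap, not in how large its effect is. It warrants a correction because a patient-level check is cheap; it does not invalidate the design.

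**What to change.** 1. Extend exclusion row 12 in Protocol Table 2 and SAP Table 3, and the SAP 6.1.2 text, to exclude any control with a detectable PrismRA order, result or claim before the index date. Search the linked claims, EMR and laboratory data, and report the number found in the patient flow diagram.
2. Add a sensitivity analysis, if the sponsor's laboratory can supply ordering-provider NPIs with first order dates: also exclude controls whose treating physician had ordered PrismRA on or before the control's index date.
3. If the linked data cannot identify the test, say so in the limitations and give a dilution range like the one above.
4. In the same edit, reconcile the scope of the existing rule. The SAP 6.1.2 text covers only the physician managing treatment initiation, while row 12 covers any trial rheumatologist who has cared for the patient.

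The cost is one added filter in a selection step that already screens by NPI and, for the sensitivity analysis, one list from the sponsor's laboratory. The documents do not confirm that such a list exists or can be shared, or that claims identify the test. Some contemporaneous controls would be lost, and tests not recorded in the linked data would still be missed.
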